
Primary aim. To compare total MPA (min/wk.) across the 6-mo. active intervention in adults with AD and their caregiver randomized to RGV and EUC. We expect greater MPA in the RGV compared to EUC arm.

Secondary aims: To compare the following across 18 mos. between RGV and EUC. *Adults with AD:* MPA (min/wk.), sedentary time (min/wk.), percentage meeting 150 min/wk. goal, functional fitness, activities of daily living (basic/instrumental), quality of life, residential transitions, neuropsychiatric symptoms, cognitive function. *Caregivers:* Total MPA (min/wk.), sedentary time (min/wk.), functional fitness, quality of life, caregiver burden. We expect more favorable changes for all secondary outcomes for both adults with AD and caregivers in the RGV compared with the EUC arm.

Exploratory aim. To evaluate the influence of process variables/ characteristics on MPA in adults with AD and their caregiver across 18 mos.: age, sex, BMI, attendance (exercise/support sessions), use of recorded sessions, PA self-monitoring, peer interactions during group sessions, caregiver support, level of dementia.

B. Background and Significance

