
Secondary outcomes. Secondary/exploratory outcomes will be assessed at baseline (1-2 wks. before starting the intervention), 6, 12 and 18 mos. in the adult with AD or caregiver's home. Our experience with similar trials suggests these assessments, which will be completed by trained staff blinded to condition, will require ~75 min to complete. Staff will receive refresher training and complete reliability assessments for all physical measures 2-3 times/yr.

Secondary outcomes-Adult with AD. Sedentary time will be assessed using data collected from the ActiGraph as described above. Functional fitness will be measured using Functional Fitness Test (FFT) previously called the Senior Fitness Test (92). The individual fitness test items involve common activities such as getting up from a chair, walking, lifting, bending, and stretching. Reliability of the FFT in older adults with cognitive impairment is high in all of the test items (ICC ≥ 0.93) (93). Activities of daily living will be assessed using the Disabilities Assessment for Dementia (DAD)(94). The DAD includes 40 items: 17 related to basic self-care and 23 to instrumental activities of daily living. DAD demonstrated a high degree of internal consistency (Cronbach's alpha = .96) and excellent inter-rater (n = 31, ICC = .95) and test-retest (n = 45, ICC = .96) reliability. In addition, it has been shown to have no gender bias. Quality of life will be assessed using the QOL-AD(95), a brief, 13-item self-report and 15-item caregiver-report. The QOL-AD has shown acceptable validity and reliability when completed by adults with AD or a caregiver proxy (ICC= .76 and .92 respectively) (95). Residential transitions, i.e., from home to institutional care, will be tracked by health coaches. We will also assess caregiver desire to institutionalize the adult with AD using the 6-item Morycz's Desire-to-Institutionalize Scale (96). This scale demonstrated moderate reliability with KR-20 alpha of .694 for Whites, .742 for African Americans, and .767 for Hispanics (97). Neuropsychiatric symptoms will be assessed using the Neuropsychiatric Inventory (NPI) (98). The NPI evaluates 12 neuropsychiatric disturbances common in dementia and the amount of caregiver distress engendered by each of the neuropsychiatric disorders. Validity

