Removal from the Study. If the study present greater then minimal risk to a participant they will be censored from the study and referred to the University of Kansas Alzheimer's Disease Center for recommendations for other resources for PA. All participants and caregivers will be informed that they may be censored from the study due to safety risk during the consent procedure. We believe the following scenarios would present a greater than minimal risk to participants. Lack of caregiver. A caregiver will be asked to participate in the intervention with the adult with AD. Many caregivers will be older adults and it is possible some may become deceased, become ill or hospitalized and unable to provide care to the AD individual. If this happens, the adult with AD will be asked to identify another individual to serve as the official study caregiver. If an alternative caregiver cannot be identified the individual with AD will be censored from the study from that time forward.

Transition to a residential facility. Some adults with AD may be placed in a residential care facility during the 18-mo. intervention. If this occurs the adult with AD will be censored from the study.

Change in severity of AD. If dementia progresses to the point that either the caregiver or research staff feel the intervention is no longer safe for the individual, they will be censored from the study. If an individual with AD is removed from the study for one of the aforementioned reasons (transition to residential facility or change in severity of AD), decides to no longer participate in the intervention, or dies during the intervention, the caregiver will be allowed to continue in the intervention, if they choose. If a caregiver stays enrolled in the intervention without the person with AD we will no longer collect outcomes regarding Caregiver Burden or Quality of the dyadic relationship.

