Secondary aim: To compare adults with AD and their caregivers randomized to RGV or ECU on the following outcomes across 18 mos. *Adults with AD:* MPA (min/wk.), sedentary time (min/wk.), percentage meeting 150 min/wk. goal, functional fitness, activities of daily living (basic/instrumental), quality of life, residential transitions, neuropsychiatric symptoms, and cognitive function. *Caregivers:* MPA (min/wk.), sedentary time (min/wk.), functional fitness, quality of life, and caregiver burden. Similar mixed models will be fitted separately for these outcome variables to examine group effect, time effect, and group-by-time interaction while controlling for the number of contacts with research staff and the baseline characteristics imbalanced between participant subgroups.

Exploratory aim: To evaluate the influence of process variables/participant characteristics on MPA in adults with AD and their caregiver across 18 mos.: age, sex, BMI, attendance (exercise/support sessions), use of recorded sessions, PA self-monitoring, peer interactions during group sessions, caregiver support, type and quality of the dyadic relationship, number of caregivers, and level of dementia. If MPA is not significantly different between RGV and EUC across 18 mos., i.e., no significant group effect or group-by-time interaction, we will combine the two arms and examine associations of the process variables/characteristics with MPA in mixed modeling. However, if a significant between-arm difference in MPA is identified, we will determine whether the process variables/characteristics enhance or attenuate the treatment effects, i.e., moderation, by testing a 2-way interaction with the group effect and/or a 3-way interaction with the group-by-time interaction term. In addition, we will examine how caregiver MPA influences the MPA of adults with AD over the 6-mo. active intervention, 6 mos. maintenance, and 6 mos. no contact. Some variables will be measured only at baseline, some will be summarized across the trial, while others will be assessed at specific time points. Thus, we will carefully design our models to assure the appropriateness of the analysis.

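### Caregiver burden stops being collected in retained caregivers once the adult with AD leaves, even if caregiving continues; the loss is avoidable, of unknown and probably small size, and cheap to fix

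*Combined protocol and SAP*

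**What the plan says.** Section F, under Removal from the Study, describes how the adult with AD may be taken out of the trial. One route is decline: "If dementia progresses to the point that either the caregiver or research staff feel the intervention is no longer safe for the individual". Another is placement: "Some adults with AD may be placed in a residential care facility during the 18-mo. intervention". Two more follow where the adult "decides to no longer participate in the intervention, or dies during the intervention, the caregiver will be allowed to continue in the intervention". The caregiver's option to stay covers all four.

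For a caregiver who stays on, the rule is: "we will no longer collect outcomes regarding Caregiver Burden or Quality of the dyadic relationship". The only condition is that the caregiver is enrolled without the adult with AD. Nothing elsewhere in the document qualifies or reverses it.

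Caregiver burden is a secondary outcome over 18 months, both in the Secondary aims ("Total MPA (min/wk.), sedentary time (min/wk.), functional fitness, quality of life, caregiver burden") and in the analysis plan ("MPA (min/wk.), sedentary time (min/wk.), functional fitness, quality of life, and caregiver burden"), with an expectation that RGV does better. It is measured by the 12-item Zarit interview, which the caregiver completes alone. On timing, "Secondary/exploratory outcomes will be assessed at baseline (1-2 wks. before starting the intervention), 6, 12 and 18 mos".

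The Missing data paragraph recognises two sources, attrition (handled by FIML) and nonresponse (handled by multiple imputation), and relies on MAR.

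**The concern.** The four exits are treated alike, but they differ in what they imply for burden. Death ends caregiving, and placement ends care at home. Removal for severity and a decision to stop the intervention end neither by themselves. In those two cases a randomised, retained caregiver may still be caring for the adult, and a questionnaire needing only the caregiver's answers is withheld by rule.

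The rule may also be informative. Dementia progression triggers one of the exits and plausibly also drives burden. If unrecorded scores tend to be higher than earlier scores would predict, mean burden is understated. If such exits are more frequent in one arm, the arm comparison is biased. Section G describes the design as intent-to-treat, and scores that were never collected cannot be recovered at analysis.

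**Working it through.** **1. Which exits leave burden defined**

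| Exit of the adult with AD | Can caregiving continue? | Link to decline in the text |
|---|---|---|
| Change in severity | Yes; nothing says it has ended | Direct |
| Decision to stop | Yes; nothing says it has ended | Not shown |
| Residential placement | Care at home has ended | Plausible |
| Death | No | Not stated |

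The rule goes further than needed in the first two rows.

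**2. Whether the caregiver is still visited.** Only two outcomes are named as dropped. By inference the caregiver's accelerometry, functional fitness and SF-36 continue at 6, 12 and 18 months. The document does not list what continues.

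**3. Whether the missing-data plan covers it.** Planned non-collection in a retained caregiver is neither dropout nor nonresponse as the plan describes them. Level of dementia (CDR) is measured only at baseline, so it cannot follow decline up to exit. Auxiliary variables are mentioned only for the imputation step. No sensitivity analysis for data missing not at random is given.

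**4. How many caregivers.** The document gives no exit rate by reason or arm. Section C assumes about 20% attrition overall; 20% of 50 per arm is 10. That is only a loose ceiling, because it includes dyads that leave entirely. The rule matters only where the adult exits, the caregiver stays, and care continues.

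**5. Possible bias.** If unrecorded burden lies k SD above its MAR prediction, and shares p(RGV) and p(EUC) are affected:

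bias in (RGV − EUC) = k × [p(EUC) − p(RGV)]

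With assumed shares of 10% and 20%, k = 0.5 gives 0.5 × 0.10 = 0.05 SD and k = 1 gives 0.10 SD. Equal shares give 0.

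To obtain k rather than assume it, I simulated earlier and current scores as bivariate normal (correlation 0.5 or 0.7), with no true arm effect, log-odds of exit rising by 1 per SD of current burden, and regression adjustment for the earlier score. All of these are assumptions.

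| Exit, RGV vs EUC | Spurious RGV − EUC difference |
|---|---|
| 10% vs 20% | 0.05 SD (correlation 0.7) to 0.06 SD (0.5) |
| 5% vs 10% | 0.02 to 0.03 SD |
| 3% vs 6% | about 0.01 to 0.02 SD |
| Equal | about 0 |

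At 20% exit in both arms, mean burden is understated by 0.09 (correlation 0.7) to 0.13 SD (0.5) in each arm.

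The extreme bound removes exactly the top 10% and top 20%, with nothing recovered from earlier scores. The mean shifts by −0.195 and −0.350 SD, a difference of 0.155 SD.

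**6. Direction.** In the 10% vs 20% case EUC loses more high-burden caregivers, so EUC looks better than it is and RGV looks worse.

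**7. Precision.** The plan gives no power figure for burden. For one time point, two-sided alpha 0.05 (assumed) and 80% power, the detectable difference is (1.96 + 0.84) × √(2/n):

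- n = 50 per arm: 0.56 SD
- n = 45 (10% lost): 0.59 SD
- n = 40 (20% lost): 0.63 SD

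The standard error of an arm difference at 50 per arm is √(2/50) = 0.20 SD.

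**The case against.** The strongest reply is about size. A bias of 0.05 to 0.06 SD is between a quarter and a third of one standard error (0.05/0.20 and 0.06/0.20) and about a tenth of the 0.56 SD detectable difference. It needs a twofold difference in exit between arms, for which the document gives no basis. It also runs against the trial's hypothesis, so in that scenario it cannot create a false benefit. The simulation treats all exits as burden-related and as preceding a single final score. The planned mixed model keeps every score taken before exit, which dilutes the effect. All of this stands, and it limits the point to a minor one.

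A reader might infer that the missing scores cannot be recovered. That is too strong: FIML uses earlier scores, the model adjusts for variables that differ between dropouts and completers, and the simulation itself shows partial recovery. The supportable wording is that recovery may be incomplete.

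A reader might also infer that these caregivers normally still live with the adult and are near their peak burden. The document says neither. Eligibility asks only for 20 hours a week together, and the background reports that 66% of caregivers co-reside.

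Stopping the dyadic relationship scale is easier to defend. It is rated from both partners' perspectives, is listed as both secondary and exploratory, and is absent from the secondary aim.

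The reply does not answer the central point: the rule ignores whether caregiving continues, and so discards obtainable data on a named secondary outcome.

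**Conclusion.** The point holds in limited form. Burden collection stops for every retained caregiver after any of the four exits, although for two of them caregiving may continue and the Zarit-12 remains meaningful. The missing-data plan does not address this case, and MAR is doubtful where the trigger is dementia progression.

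The size cannot be computed from the document. About 0.05 to 0.06 SD of arm bias rests on an assumed 10% vs 20% burden-related exit; it falls with fewer affected caregivers and is about zero if exit is equal. There is also some loss of precision. It is tempting to read the 20% attrition figure as 10 of 50 caregivers per arm losing burden data while still enrolled. The document does not support that, because the figure is overall attrition used in the power calculation for physical activity. That follow-up visits continue for these caregivers is an inference. The case rests on caregiver burden; the dyadic scale adds little.

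**What to change.** Replace the sentence under Removal from the Study with wording to this effect: for caregivers who remain enrolled, the Zarit-12 (and optionally the caregiver-rated dyadic relationship scale) continues at 6, 12 and 18 months while the adult with AD is alive and the caregiver reports still providing care, whatever the reason the adult left. Collection stops only at death or the end of caregiving, with date and reason recorded. State what counts as still providing care, particularly after placement.

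In the analysis plan, include all collected scores in the assigned arm, and report by arm how many caregivers were truncated and why.

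The cost is a one-sentence amendment and a few minutes of questionnaire time for a small number of caregivers, at visits they should already have. It changes data collection only. Truncation at death or the end of caregiving remains, and the reported counts would show how much of it there is.

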Orientation. One week prior to initiating the intervention, health coaches will conduct a home visit (~60 min) with each adult with AD/caregiver dyad in both intervention arms. Health coaches will deliver all necessary equipment and orient participants to the use of all equipment/software, answer questions regarding the general requirements of the trial, and demonstrate/practice the basic aerobic and resistance exercises with participants. Each dyad will be provided with the following: iPad®, iPod® touch, 2- Fitbit Versa Lites® and resistance bands (TheraBand, Akron, OH). The iPad® will be used to deliver either the real time exercise sessions (RGV only), individual support sessions, and for syncing the Fitbit of adults with AD. The iPod® will be used to sync the Fitbit of caregivers, as the iPad® is capable of syncing only one Fitbit. The iPod® will also allow for communication between the caregiver and the health coach via iMessage. Dyads in the RGV arm will be provided with an iPad®/HDMI adaptor, which allows video conference sessions to be displayed on a larger TV screen, if desired. All software/apps appropriate for each intervention arm will be loaded on the iPad®/ iPod®, i.e., Zoom®, Dropbox® (to provide access to recorded videos and written materials) and Fitbit app. Reminders regarding upcoming group video and/or health educator/dyad support sessions will be programmed using the iCalendar app on the iPad®. Access to non-study related materials, e.g., web browsing, app store etc. will be blocked on all iPads®/ iPods® until completion of the maintenance intervention (12 mos.). Individual support sessions. Dyads will be asked to attend 15-20-min education/support sessions (2 sessions/mo. during the active intervention (0-6 mos.) and 1 session/mo. during maintenance (7-12 mos.) delivered remotely on the iPad® using FaceTime®. No individual support sessions will be scheduled during the no-contact period (13-18 mos.). Sessions will be designed to educate and support the adult with AD and caregivers with meeting their 150 min/wk. goal for MPA. Each session will include a review of physical activity self-monitoring data, goal setting, strategies to increase and support MPA, and discussion of a topic relevant to MPA. During the active intervention (0-6 mos.) topics will include the importance of MPA for health and function, how to include MPA in the daily schedule, reduce barriers to physical activity, appropriate types of activity, creating a safe environment for physical activity, alternative activities for inclement weather, importance of hydration, etc. During maintenance (7-12 mos.) the discussion will focus on strategies to ensure continued participation in MPA, opportunities for physical activity in the community, and continued encouragement of dyadic activity. Topic outlines and information relative to support sessions will be pre-loaded on the iPad® where they can be assessed at any time across the 18-mo. trial. Self-monitoring-physical activity. Adults with AD and caregivers in both arms will be asked to wear a Fitbit Versa Lite activity tracker on their non-dominant wrist over the duration of the 18-mo. trial. This request may appear onerous; however, wearing the Fitbit is akin to wearing a wristwatch. Real-time data from the Fitbit is automatically transferred, via the web, to cloud storage (Fitabase, Small Steps Labs LLC, San Diego, CA), thus, participant burden is minimal. Fitbit data is available to both participants and the health coach via the Fitbit app. Immediate participant feedback of daily steps, minutes of sedentary time, and time spent in light, moderate and vigorous physical activity will be available via a graphic display on the device and the Fitbit app. The health coach will log into each participant account once per week to verify they are wearing and charging the device and to monitor participant activity solely for use in providing motivation and feedback during the individual support sessions. Outcome data for MPA and sedentary time will be assessed by accelerometer as described subsequently. Dyads will be reminded to wear and charge the Fitbit during group exercise (RGV only) and individual support sessions, and will receive automatic reminder messages every 3 days via the iPad® using the iCal app. We successfully used the Fitbit and these reminder procedures in our pilot trials in adults with AD (44) and similar procedures have been used by others (60).

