
RGV arm

Schedule. Group exercise sessions will be scheduled on 3 non-consecutive days/wk.(M,W,F) during the active intervention (0 to 6 mos.) and 1 day/wk. during maintenance (mos. 7-12). Group sessions will not be scheduled during the no-contact period (13-18 mos.). During orientation sessions, dyads will be asked to provide times of the day, between 10 a.m. and 7 p.m., that would be most convenient to complete the group sessions. Based on this information we will offer dyads in each cohort the choice between 2 potential session times each day. Prompts reminding adults with AD/caregivers of upcoming sessions will be sent using iMessage on the iPad® (adult with AD)/iPod® (caregiver) and iCalendar. Session delivery. Real-time exercise sessions will be delivered to adults with AD/caregiver dyads in their home by a trained health coach experienced in working with adults with AD using Zoom® video conferencing software. This software allows multiple users to see and interact with each other and the health coach via the iPad®. The health coach will conduct exercise sessions from our remote-delivery exercise studio (see facilities) which we used for remote delivery of exercise in our AD pilot (61) and in trials with adolescents with intellectual and developmental disabilities (IDD) (62), and adults with Down Syndrome (63). Tutorials describing trouble shooting for common technical problems with the Zoom® software, e.g., internet connectivity etc., will be loaded on the iPad®. Dyads with technical issues during the intervention may also contact research staff by phone or email. An alternative caregiver (other family member, staff etc.) may participate in the event that the caregiver enrolled in the trial is unable to attend an exercise session. These procedures were used in our AD pilot trial where alternative caregivers attended 8% of sessions (61). MPA session content. [name], a physical therapist, will develop the exercise program for this trial. He developed the exercise content for our pilot trial in adults with AD and has been involved in other exercise trials for adults with AD (R01AG034614, R01AG033673) (64-66). Each session will include a warm-up (~5 min), moderate intensity aerobic activity (3-5 METs) (~30 min), resistance and balance/coordination exercise (~5 min.), and cool-down/stretching (~5 min.). The MPA portion will ramp from 10 min/session at wk. 1 to the goal of 30 min/session at wk. 8. Each session will include aerobic activity, e.g., walking/jogging standing in place or sitting in a chair, sit to stand, dance movements; resistance exercise, e.g., TheraBand®-arm curls, leg extensions, side leg raises, and seated rows; and balance exercise, e.g. heel to toe walks, balance walk, and standing on one foot with/without support of a chair). [name] will provide modifications for participants having difficulty with any specific exercises. Health coaches will encourage interactions between participants during group sessions and ensure interactions between participants do not focus on dementia (67), but rather on issues relative to supporting their peer's efforts to increase MPA. Additionally, the Zoom app used for the sessions allows for messaging between participants during and after the group exercise sessions. Caregivers will be allowed to message the research staff and other caregivers for help and support both during the sessions and outside of the group sessions. We will keep copies of the messages sent to research staff on the KUMC P-Drive. Outside session MPA. Group exercise sessions will provide the potential to accumulate 90 min/wk. (3 sessions x 30 min/session) during the active intervention (0-6 mos.) and 30 min/wk. (1 session) during maintenance (7-12 mos.). Thus, MPA in addition to that accumulated in group sessions will be required to meet the MPA goal of 150 min/wk. To provide a transition from a sedentary to a more physically active lifestyle we will recommend goal of 45 min of MPA/wk. at wk. 1 and increase the goal by 15 min/wk.to reach the 150 min/wk. goal at wk. 8. We successfully used this MPA progression in previous trials in adults with AD (57). At the completion of each group session health coaches will provide a "weekly challenge" for participants to try a new activity or create and perform a new exercise routine etc. in order to reach the 150 min./wk. goal. Additionally, the NIA pamphlet "Exercise and Physical Activity: Your Everyday Guide" will be loaded on the iPad to assist participants in meeting the 150 min./wk. goal. Video recordings. Video recordings of all group exercise sessions will be uploaded to Dropbox®. Participants/caregivers will be encouraged to access video recordings using their iPads®/iPods® to assist with meeting the 150 min./wk. goal. Frequency and duration of participant/caregiver video access will be tracked using Dropbox® analytics. No contact follow up (13-18 mos.). Group video and individual support sessions will be discontinued. Participants will be

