Potential Benefits of the Proposed Research to the Subjects and Others. The benefits to the participants are the well-established benefits of PA including improvements in activities of daily living and mobility and may improve general cognition and balance in adults with AD. Additionally, caregivers may benefit from reduced caregiver burden and increased quality of life. Individuals with AD and caregivers may benefit from an increased understanding regarding how to develop PA routines, the benefits of regular PA, and ways to encourage PA in the household. The information obtained from this study will increase our understanding regarding strategies for the delivery of PA interventions to individuals with AD and caregivers. The risks to participants in this study are minimal while the benefits to individuals with AD and caregivers in need of increased MVPA are potentially large.

Importance of the Knowledge to be Gained. Individuals with AD and caregivers have low rates of PA and may benefit greatly from participation in a PA program. The development of an effective strategy for increasing PA would be important for improving physical function, mobility, and quality of life in adults with AD and their caregivers, resulting in allowing individuals with AD to stay in their homes longer and reducing caregiver burden. Thus, we believe adults with AD and their caregivers deserve to be included in the development of state-of-the-art interventions to improve their mobility and quality of life and believe this proposal offers a potentially viable strategy for increasing MVPA in this population.

G. Assessment of Subject Safety and Development of a Data and Safety Monitoring Plan

Adverse Event and Serious Adverse Event Collection and Reporting. Staff involved in performance of the protocol are expected continually monitor participants for adverse events throughout all outcome's assessment, exercise sessions, and individual education session. Expected side effects of exercise such as mild soreness that resolve in a reasonable short amount of time (less than 48 hours) will not be considered an AE.

Adverse Event Grading. This study uses the definition of adverse events (AE) from the "NIA Adverse Event and Serious Adverse Event Guidelines, Version 3 December 2013". AE are defined as any untoward or unfavorable medical occurrence in a human subject participant, including any

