abnormal sign, symptom, or disease, temporally associated with the participants' involvement in the research, whether or not considered related to participation in the research.

The MPIs will determine the severity and relatedness of the AE to the intervention and be responsible for reporting to the National Institute on Aging (NIA), and Safety Officer (SO) in the appropriate time frames. Severity of the adverse event will be determined using the National Cancer Institute Common Terminology Criteria for Adverse Events (CTCAE) v3.0. The intervention and measurement protocols proposed for this study pose minimal risk to participants. Because of this low risk status, the data safety monitoring plan (DSMP) for this trial focuses on close monitoring by the multiple principal investigators (MPI) and the safety officer along with prompt reporting of excessive or serious adverse events to the NIH and to the Human Subjects Committee (HSC) at The University of Kansas Medical Center.

Adverse Event Reporting The MPIs will review and evaluate adverse events within 72 hours. All adverse events, regardless of their seriousness, severity or relatedness to the intervention are reportable to NIA PO and the Safety Officer (SO) semi-annually. A summary of these reports is provided to the IRB on an annual basis. Deaths and SAEs are handled in an expedited fashion as follows:

- Deaths: All deaths will be reported within 24 hours to the NIA Program Officer, SO, and the IRB.
- Unanticipated SAEs: When SAEs occur that are unanticipated and related to the intervention, they will be reported to the NIA Program Officer, ISO, and the IRB within 48 hours of study team's knowledge of the SAE.
- Other SAEs: The summary of all other SAEs will be reported to the NIA Program Officer and SO quarterly.

All potential Adverse Events will be collected on an Adverse Event Form. If study staff, tester, participant, or other individual interacting with the participant during the testing visits, group exercise session, or individual education sessions reports adverse events or complaints, relevant information will be collected and documented using REDCap.

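### Adverse events are picked up at study contacts, which RGV has far more of than EUC, so minor, short-lived events may be recorded more often in RGV and missed in EUC at equal true rates

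*Combined protocol and SAP*

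**What the plan says.** Section G, under Adverse Event and Serious Adverse Event Collection and Reporting, expects staff to "monitor participants for adverse events throughout all outcome's assessment, exercise sessions, and individual education session". Under Adverse Event Reporting, the form is completed when someone interacting with the participant "during the testing visits, group exercise session, or individual education sessions reports adverse events or complaints". Expected effects such as mild soreness that clears in under 48 hours are not counted as AEs.

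The contact schedules are as follows.

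- **Group sessions, RGV only** (RGV arm, Schedule): "3 non-consecutive days/wk.(M,W,F) during the active intervention (0 to 6 mos.) and 1 day/wk. during maintenance (mos. 7-12"). For the last period, "Group sessions will not be scheduled during the no-contact period (13-18 mos").
- **Individual support sessions, both arms** (Intervention components common to both arms): "2 sessions/mo. during the active intervention (0-6 mos.) and 1 session/mo. during maintenance (7-12 mos"). For the last period, "No individual support sessions will be scheduled during the no-contact period (13-18 mos").
- **Testing visits, both arms** (Secondary outcomes): "Secondary/exploratory outcomes will be assessed at baseline (1-2 wks. before starting the intervention), 6, 12 and 18 mos". The 3-month accelerometer is mailed, so it is not a visit.

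The listed content of a support session covers self-monitoring review, goal setting, strategies and an activity topic. AE enquiry is not on that list. All AEs go to the NIA Program Officer and the Safety Officer twice a year, and the IRB receives an annual summary.

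**The concern.** Detection depends on contact, and contact differs by arm by design. An RGV participant with a strained calf sees a coach within days and may mention it or be seen limping. An EUC participant with the same strain exercises at home, and the next scheduled call may be two to four weeks away, by which time the strain may be gone or forgotten. Recall is a fair worry here: the adults with AD may enter with an MMSE as low as 11, and a caregiver qualifies with 20 hours a week of shared time.

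Two errors follow. RGV may look less safe than it is relative to EUC, and minor injuries during unsupervised EUC exercise may go unrecorded and give false reassurance. The plan already treats unequal contact as important for efficacy: the models under Statistical and Data Analysis control for the number of staff contacts. Nothing equivalent is stated for AEs.

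**Working it through.** The documents give no contact total, contact ratio or AE rate, so there is no stated figure to reproduce.

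**Step 1. Scheduled sessions per dyad**, taking 26 weeks per six months. Allocation is 1:1, so per-dyad ratios are also per-arm ratios.

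| Period | RGV | EUC | Ratio |
|---|---|---|---|
| Months 0-6 | 3×26 + 12 = 90 | 2×6 = 12 | 7.5 |
| Months 7-12 | 26 + 6 = 32 | 1×6 = 6 | 5.3 |
| Months 0-12 | 122 | 18 | 6.8 |
| Months 13-18 | 0 | 0 | – |
| 18 months, with the 6-, 12- and 18-month visits | 122 + 3 = 125 | 18 + 3 = 21 | 6.0 |

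At the pilot's attendance (77% for group sessions in adults with AD, 87% for support sessions), months 0-12 give 0.77×104 + 0.87×18 = 95.7 against 0.87×18 = 15.7, a ratio of 6.1. With the three visits added it is 98.7 / 18.7 = 5.3.

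**Step 2. A hand check of what this could do to counts.** Assume an event surfaces only if a contact falls within 7 days of it, and then surfaces with certainty.

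- Months 0-6: EUC has one call per 182/12 = 15.2 days, so it captures 7/15.2 = 46%. RGV sessions on Monday, Wednesday and Friday capture essentially all. Ratio 1/0.46 = 2.2.
- Months 7-12: EUC has one call per 182/6 = 30.3 days and captures 7/30.3 = 23%. Weekly RGV sessions still capture nearly all.
- Months 0-12 together, with equal event rates in each half: (1 + 1)/(0.46 + 0.23) = 2.9.

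**Step 3. Range over the assumption.** The 7-day window has no source in the documents, so it was varied. The model takes equal true rates, onset uniform over 18 months, pilot attendance at sessions and full attendance at the three visits. Each attended contact within W days after onset surfaces the event with probability p. W and p are assumptions.

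| W (days) | p | Captured, RGV | Captured, EUC | Recorded ratio, 18 months |
|---|---|---|---|---|
| 3 | 0.1 | 0.05 | 0.01 | 5.1 |
| 7 | 0.5 | 0.43 | 0.12 | 3.6 |
| 14 | 0.5 | 0.57 | 0.23 | 2.5 |
| 30 | 0.5 | 0.66 | 0.41 | 1.6 |
| 30 | 0.9 | 0.71 | 0.64 | 1.1 |
| 90 | 0.9 | 0.81 | 0.81 | 1.0 |

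Ratios come from unrounded capture fractions. Over the full grid (W from 3 to 180 days, p from 0.1 to 1.0) the ratio ran from about 1.0 to 5.1 and never fell below 1. The lower bound is structural: the RGV schedule contains every EUC contact plus the group sessions, so at equal attendance at the shared contacts RGV cannot capture less.

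**The case against.** The strongest reply is that the consequence is inferred. Safety is neither an aim nor an outcome, no AE comparison is planned, and the reporting passages do not mention a split by arm. Section G calls the trial minimal risk and names failure to recruit or deliver as the likeliest reason to stop. This stands: by-arm AE tables are a reasonable expectation for a two-arm trial, but the documents do not promise one.

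Second, a reader might infer that nobody asks EUC participants about AEs. The documents do not support that. Staff are told to monitor at assessments and individual sessions, which both arms share. The AE form and the Safety Officer's checklists are not in the available text, so whether either contains a prompt is unknown. What can be said is that no common solicited question is described.

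Third, other routes exist. Caregivers in both arms can message staff, and coaches check Fitbit accounts weekly. The 48-hour soreness rule also removes some of the most contact-sensitive events. These points reduce the asymmetry. They do not remove it, because messaging is optional and neither messaging nor the Fitbit check is an AE query.

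Fourth, one might want to restrict the by-arm comparison to the contacts both arms share. That would overcorrect. An injury witnessed in a group session and later forgotten would drop out, although harm caused by supervised exercise is a true harm of RGV.

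**Conclusion.** The point holds as a risk of differential ascertainment. RGV has 6.8 times as many scheduled intervention sessions as EUC in months 0-12 (7.5 times in months 0-6), and 6.0 times as many contacts over 18 months with the post-baseline visits. The imbalance arises in months 0-12, since neither arm has sessions afterwards.

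A reader might infer that AE counts are certain to look worse in RGV, or to be inflated about sevenfold. Neither follows. The contact ratio is not the AE ratio. The AE ratio depends on how long an event lasts and how well it is recalled, which the documents do not give. It spans about 1.0 to about 5 under the assumptions shown, and is near 1.0 for lasting or well-recalled events. Deaths and most SAEs should be little affected; the exposure is in minor, short-lived events.

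No planned hypothesis test is affected. The consequence falls on the safety reports, including any judgement that AEs are excessive, and on any by-arm AE table. It justifies a cheap improvement to AE collection.

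**What to change.** 1. Ask the same scripted AE question in both arms, with a look-back to the previous shared contact, at every individual support session and at the 6-, 12- and 18-month visits. This gives 18 + 3 = 21 solicited opportunities per dyad in each arm. Ask it in RGV even when an event is already known from a group session, so that the shared-contact count is comparable.
2. Add a source field to the AE form (support session, testing visit, group session, message, other). Let it show where the event was first detected and whether it was also elicited at a shared contact.
3. Report all AEs by arm. Alongside, show the by-arm count of AEs elicited at the shared contacts. Identify group-session-detected AEs by source, and keep them in the overall comparison.

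The cost is a few minutes per call at contacts already scheduled and one extra form field. More minor AEs will be recorded, mainly in EUC. No extra visits are needed.
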